3.2 Part B and C

3.2.1 Study Design Part B

The study CMCS110X2201 Part B is a randomized, double-blind, placebo-controlled, parallelarm, exploratory PoC clinical trial with 2:1 randomization of MCS110 to placebo for the first dose followed by open-label multiple doses. Part B first dose will be administered double-blind, placebo-controlled. All patients will receive active treatment after the first dose and the study will continue as an open label study.

Day 1 blinding will be maintained until week 12, which corresponds to the fourth dose for the potential Day 1 MCS110 patients. After patient reaches week 12 (Visit 7), Day 1 treatment received by the patient will be un-blinded in order to allow Day 1 placebo patients to receive a fourth dose of MCS110.

If patient received placebo at Day 1, then, the patient will follow Assessment Schedule Part B1 after Visit 7.

If patient received MCS110 at Day 1, then, the patient will follow Assessment Schedule Part B2 after Visit 7.

In the multiple dose Part B patients receive up to 4 doses of 10 mg/kg MCS110 administered once every 4 weeks. Two additional MCS110 doses will be administered, if MCS110 is well tolerated and if a reduction in tumor volume of >50% can be demonstrated after the 3^{rd} MCS110 dose by MRI taken before the 4^{th} dose.

Confidential

The primary outcome of Part B of the study will be tumor volume after multiple doses of MCS110 monitored by MRI. The primary outcome will be assessed 8 weeks after the last dose of MCS110, a time point, where free drug is expected to decline rapidly, based on modeling and simulations of free MCS110 concentrations.

Patients who meet the eligibility criteria at screening will be admitted to baseline evaluations. All baseline safety evaluation results must be available prior to dosing. Safety assessments will include physical examinations, ECGs, vital signs, standard clinical laboratory evaluations (hematology, blood chemistry, urinalysis) adverse event and serious adverse event monitoring. This study will be carried out primarily in the out-patient setting.

In order to monitor the duration of the tumor size reducing effect of MCS110, patients will have follow-up visits every 3 months for up to 2 years to document changes in growth of the residual tumor or to detect recurring tumor by MRI. The time intervals of 3 months are according to the standard of care for patients, who had undergone surgery.

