In case of relapse or regrowth of residual PVNS tumor during the follow-up period, patients will be offered to start another treatment course once the previous MCS110 treatment was longer than 6 months ago (Figure 3-3), then the patient will follow Assessment Schedule Part B re-dosing. At any time during the study, investigator and/or patient can decide to undergo surgery if patient's PVNS conditions require such a treatment.

Total enrollment in the study (Part A and Part B) will proceed until up to 18 evaluable patients have been recruited, where Part B "evaluable" patient is defined as completing the protocol until at least 2 doses of MCS110 were administered and a follow-up MRI was performed. Patients will only be eligible for the study, if they have at least one tumor site that can be measured by MRI. MRI of PVNS provides unique features depicting the extent of the tumor, synovial proliferation, joint effusion, bone erosion and deposits of hemosiderin (Cheng et al 2004; Steinbach et al 1989; Frick et al 2007; Murphey et al 2008). Part A is completed, seven patients received a single dose of MCS110 or placebo. In the multiple dose Part B, patients can be treated with up to 6 doses of MCS110 following IRB approval of the amended protocol CMCS110X2201-v04.

[figure not shown]
[figure not shown]
[figure not shown]

Figure 3-2 Study design Part B

Dosing day – 1hr i.v. infusion
 Primary Endpoint – Tumor volume reduction measured by MRI [Time-point: last MCS110 dose + 8 weeks]
 Follow-up on relapse every 3 months until up to 2 years based on MRI and symptoms
 Double-blind: only at Day 1 – Day 1 Double blind maintained until week 12

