Eligibility criteria and safety assessments will be similar as in Part B. Patients will also be followed up to 2 years Corporate Confidential Information or 1.5 years Corporate Confidential Information or 1.5 years every 4 months and they will be offered another treatment course with 10 mg/kg of MCS110 in case of relapse, where relapse is diagnosed at least 6 months after the last MCS110 dose received during the first treatment course (Figure 3-3). Then, the adult and adolescent patients will follow Assessment Schedule Part C re-dosing.

Efficacy assessments will include tumor volume reduction,

, joint-specific questionnaires, VAS and time to relapse.

Conditions of lower dose arm recruitment extension

If a lower dose is identified with at least the same efficacy as 10 mg/kg, defined as tumor volume reduction evaluated by MRI of at least 45%, additional patients may be enrolled in this lower dose group to extend the arm up to approximately 10 patients. Only one dose level, either 3 or 5 mg/kg may be extended and the additional patients will be allocated to the selected dose level in an open label fashion with the same Assessment schedule Part C applied, Corporate Confidential Information

[figure not shown]
[figure not shown]

Figure 3-4 Study design Part C – adults and adolescent (Amendment 7)

Figure 3-5 Study design Part C – adults and adolescents (Amendment 6)

As some patients will have followed study design of Amendment 6 we keep it in the protocol.

Confidential

The planned enrollment number in Part C is approximately 15 patients. If a lower dose is identified to be, at least, as efficacious as 10 mg/kg, additional patients may be enrolled in open label to extend the efficacious 3 mg/kg or 5 mg/kg arm to approximately 10 patients.

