If a patient develops periorbitalswelling, subsequent dosing (e.g., 4 wks, 8 wks) will be put on hold until one week after the swelling has resolved.

If a patient develops any adverse event considered as drug related by the investigator, which has not resolved before the following dose, next dosing will be delayed until considered resolved.

If there are abnormal hematology and / or biochemistry laboratory values (CTCAE grade 3) judged as clinically significant by the Investigator, the next dose will be delayed until abnormalities have resolved. Isolated CK increase with normal troponin T and aldolase is not considered a safety concern even if reaching CTCAE grade 3.

Part B: If dosing of 4 times 10 mg/kg MCS110 (once every 4 weeks) is exceeding the initial 13 weeks dosing period, (due to occurrence of AEs) further dosing will be allowed up to week 20 if all AEs had resolved for more than a week and efficacy assessment demonstrates response to treatment (>50 % of tumor volume reduction after 3^{rd} dose in Part B, 45% in Part C) of these patients.

Dosing extension to 6 consecutive doses once every 4 weeks

Patients initially receive 4 consecutive doses once every 4 weeks (week 0, 4, 8, 12). Patients will receive 1 or 2 additional doses under the following conditions:

- no treatment related safety issues (for periorbital swelling* only if >grade 2) resulting in dosing delay during the first 4 doses the tumor has not been completely eliminated after the 3rd dose [determined by MRI at week 12]
- the tumor did respond to treatment (Part B: >50 % tumor volume reduction) after the 3rd dose [determined by MRI at week 12] Corporate Confidential Information

In Part C additional criteria apply as following:

- Part C (arms 3 mg/kg or 5 mg/kg): the tumor did respond to treatment (≥45 % tumor volume reduction) after the 3rd dose [determined by MRI at week 12] and MCS110 was tolerated: the patient will receive 3 additional doses of the same as dose level
- Part C (arms 3 mg/kg or 5 mg/kg): the tumor response to treatment is <45 % of tumor volume reduction after the 3rd dose [determined by MRI at week 12] and MCS110 was tolerated: the patient will receive doses increased to 10 mg/kg
- Part C (arm 10 mg/kg): the tumor did respond to treatment (≥45 % tumor volume reduction) after the 3rd dose [determined by MRI at week 12] and MCS110 was tolerated: the patient will receive 3 additional doses of 10 mg/kg

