- Part C (arm 10mg/kg): the tumor response to treatment is <45 % of tumor volume reduction after the 3rd dose [determined by MRI at week 12] and MCS110 was tolerated: the patient can receive 1 additional dose of 10 mg/kg

New treatment course in case of recurrence of tumor or regrowth of residual tissue

If, based on MRI, relapse is identified, it is possible to start an additional course of 6 consecutive doses of MCS110 10 mg/kg, if there was:

- Good tolerability of MCS110 during the first treatment cycle
 - Patient received 6 doses
 - No early treatment discontinuation

- Good response in tumor volume reduction: Tumor volume reduction at (up to) 1°EP (8 wks post last dose of 6 doses) of >50% during the 1st treatment cycle
- Relapse defined as:
 - Symptoms (pain, swelling, redness, stiffness) and
 - Tumor volume increase greater than 50% of the difference between tumor volume at BL and the lowest tumor volume measured by MRI.
- Last dose of MCS110 was at least \geq 6 months ago.
- Inclusion/exclusion criteria are still fulfilled.

During the second treatment course safety monitoring will be the same as during the first treatment course. Efficacy will be assessed by MRI after the 3rd dose at week 12 to decide on dosing beyond 4 doses and then again 8 weeks post last dose. Once a lower dose with same efficacy as 10 mg/kg has been identified in Part C, relapse patients will receive the lower dose treatment. During the second treatment course no placebo dose will be administered.

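### Under Protocol 5.5.5.2, a patient stopped at 4 doses because the tumour was gone at week 12 fails the 6-dose condition for re-treatment on relapse; the sections also disagree on who stops at 4

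*Protocol*

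**What the plan says.** Two consecutive parts of Protocol 5.5.5.2 matter here.

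- **Extension beyond 4 doses.** All patients start with 4 doses, at weeks 0, 4, 8 and 12. One or two more follow under listed conditions: no treatment-related safety delay, a sufficient response, and that "the tumor has not been completely eliminated after the 3rd dose [determined by MRI at week 12". Additional criteria are then given for Part C.
- **New course on relapse.** Good tolerability is itemised as "Patient received 6 doses" and no early discontinuation. Good response is a volume reduction at, or up to, the primary endpoint ("8 wks post last dose of 6 doses) of >50% during the 1st treatment cycle"). Relapse needs symptoms and "Tumor volume increase greater than 50% of the difference between tumor volume at BL and the lowest tumor volume measured by MRI". At least 6 months must have passed since the last dose, and the entry criteria must still be met.

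The design sections describe the offer more broadly. Section 3.2.1 (Part B) says that "patients will be offered to start another treatment course once the previous MCS110 treatment was longer than 6 months ago". Section 3.2.2 (Part C) says that "they will be offered another treatment course with 10 mg/kg of MCS110 in case of relapse", for relapse diagnosed at least 6 months after the last dose. Neither mentions a dose count.

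The extension is also stated elsewhere with no exception for elimination. For Part B, 3.2.1 says: "Two additional MCS110 doses will be administered, if MCS110 is well tolerated and if a reduction in tumor volume of >50% can be demonstrated". For 3 and 5 mg/kg in Part C, the 5.5.5.2 bullet says that at a reduction of 45% or more "the patient will receive 3 additional doses of the same as dose level"; 3.2.2, the synopsis and SAP 2.4 agree. The 10 mg/kg bullet likewise gives 3 more doses, while for that arm 3.2.2 refers back to 5.5.5.2 and the synopsis to the Part B criteria.

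**The concern.** Taken together, the two rules in 5.5.5.2 penalise the best early response. Dosing stops at 4 because the drug has worked, and the count of 4 then closes the door to re-treatment. Complete ablation is the stated goal of multiple dosing (Sections 1.4 and 3.2.3), so the patients excluded are those who reach that goal soonest.

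At stake is one decision for an individual patient: refusal of a second course that the design section says will be offered, in a disease for which the protocol reports no approved drug. A site could not simply use its judgement, because Section 11 permits no authorised deviations. Section 4 has Part B patients remaining in follow-up alongside Part C, so the question could still arise.

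**Working it through.** The plan gives no figure to reproduce. The check traces the rules and adds a little arithmetic.

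**Trace under 5.5.5.2 (Part B patient given MCS110 on Day 1)**

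| Step | Rule | Result |
|---|---|---|
| 1 | Base course | 4 doses, the last at week 12 |
| 2 | No tumour on the week 12 MRI | Extension condition fails: 4 + 0 = 4 doses |
| 3 | Re-dosing needs 6 doses | 4 is not 6: fails |
| 4 | No early discontinuation | Can be met |
| 5 | Reduction above 50% at or up to the primary endpoint | 100% at week 12; can reasonably be read as met |
| 6 | At least 6 months since last dose | Met from about week 12 + 26 = 38 |

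Only step 3 plainly fails, and it fails because of step 2 rather than through any tolerability or response problem.

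**The same patient under 3.2.1.** A reduction of 100% exceeds 50%, so the patient receives 4 + 2 = 6 doses and step 3 is met. The bar therefore depends on whether 5.5.5.2 or 3.2.1 governs.

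**Part C.** The elimination condition stands in the general list of 5.5.5.2, and the Part C items are introduced as additional to it. On that reading a complete responder stops at 4. Read alone, the Part C bullets give 3 + 3 = 6 doses at a reduction of 45% or more. The dose count is thus ambiguous in both parts.

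**How demanding the relapse definition is.** The required increase is more than 0.5 × (baseline − lowest volume). With a lowest volume of 0, this is 0.5 × (baseline − 0), or more than 50% of baseline volume, with symptoms as well.

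**Time available.** On Schedule B2 the primary endpoint MRI falls at week 12 + 8 = 20, and MRI follow-up runs to week 96. Re-treatment becomes possible from about week 38. In Part B the 6 months limit when re-treatment may start, not when relapse is found, so a relapse seen at week 24 or 36 could qualify later. Only 3.2.2 attaches the 6 months to diagnosis.

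**How many patients.** The introduction reports 11 patients exposed in Part B and 18 in Part C, so 11 is the ceiling for Part B and 11 + 18 = 29 if the elimination condition also covers every Part C arm. The documents give neither the proportion with no tumour at week 12 nor the relapse rate among them. Section 1.4 reports an average reduction of about 50% after three 10 mg/kg doses in Part B, which suggests that elimination by then is uncommon.

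**The case against.** The strongest reply is that the 6-dose condition is deliberate. It is listed under good tolerability, the second course is planned as six doses of 10 mg/kg, and four drug-related serious adverse events had been reported. A patient who had only 4 doses has not shown tolerance of 6. That is true and should be named as a small downside of the fix. It does not justify the bar, because the protocol itself treats four doses without a safety-related delay as enough to go on to doses 5 and 6. It also keeps the same safety monitoring and repeats the week 12 decision in the second course.

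A second reply is that 3.2.1 and 3.2.2 are overviews that also omit the tolerability, response and entry conditions, and that the Part B re-dosing schedule says patients proceed if eligible. This stands in part: silence in an overview is not a contradiction. But the dose count differs from those conditions, since here the protocol's own stopping rule makes it impossible to meet. SAP 2.3 repeats the offer but still describes up to 4 doses, so it says little about intent under a six-dose rule.

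Two stronger readings are tempting.

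- A reader might infer that the bar is certain in Part B. It is not: 3.2.1 would take the same patient to 6 doses, and text is redacted directly after the general extension conditions. Re-dosing footnotes and Figure 3-3 are also not available.
- A reader might take the response criterion as a second bar, because it too refers to 6 doses. The words allowing reduction up to the primary endpoint make that doubtful.

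**Conclusion.** The gap is real on the wording of 5.5.5.2: elimination at week 12 leads to 4 doses, and 4 doses fail the re-dosing criterion despite full response and good tolerability. This is at odds with the offer in 3.2.1. Beneath it lies an inconsistency in both parts over whether elimination stops dosing at 4. The conclusion assumes that 5.5.5.2, as the detailed text, governs, and that no redacted text supplies an exception.

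For an affected patient the difference is re-treatment barred or possible, although 3.2.1 leaves surgery available in Part B at any time. The case is rare. A reader might attach a probability to it, but any such figure would only restate guessed rates. The sponsor already holds the Part B three-dose results and can say whether anyone is affected; possibly nobody is. No planned efficacy comparison changes. This is a minor correction to individual re-treatment eligibility.

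**What to change.** 1. In the re-dosing criteria of 5.5.5.2, replace the 6-dose condition with: received 6 doses, or 4 doses where the only reason for not extending was complete tumour elimination at week 12.
2. In the response criterion, refer to the last dose of the first course instead of the last of 6 doses.
3. Keep the tolerability, no-early-discontinuation, relapse, 6-month and inclusion/exclusion conditions. Patients held at 4 because of a safety-related delay then stay excluded.
4. Make 3.2.1 and the Part C bullets agree with 5.5.5.2 on whether elimination at week 12 stops dosing at 4, and carry the answer into 3.2.2, the synopsis and SAP 2.4. If the sponsor decides that elimination does not stop dosing, item 1 is still needed for anyone already stopped at 4.

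The cost is a few sentences, with no new visits or data. Section 11.1 requires a written amendment, so the change can go into the next one.

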5.5.6 Rescue medication

Not applicable.

5.5.7 Concomitant treatment

The investigator should instruct the patient to notify the study site about any new medications he/she takes after the start of the study drug. All medications and significant non-drug therapies (including physical therapy and blood transfusions) administered after the patient starts treatment with study drug must be listed on the Concomitant medications/Significant non-drug therapies after start of study drug eCRF.

All prescription medications and over-the-counter drugs taken within the timeframe defined in the entry criteria prior to the start of the study and during the study, must be recorded on the Concomitant Medications/ Non-Drug Therapies page of the eCRF.

Medication entries should be specific to trade name, the single dose and unit, the frequency and route of administration, the start and discontinuation date and the reason for therapy.

Allowed medication

- Adjuvant radiation therapy as clinical standard of care after surgery (only for Part A).
- Patients on treatment with cholesterol lowering medication or anti-hypertensives can continue with their medication, but it must be documented in the Concomitant medications / Significant non-drug therapies page of the eCRF.
- Diabetes drugs (in Part C)
- If needed, paracetamol / acetaminophen and NSAIDs (Non-Steroidal Anti-Inflammatory Drugs) are acceptable, but must be documented in the Concomitant medications / Significant non-drug therapies page of the eCRF. NSAIDs must be discontinued prior to surgery according to local practice. All pain medication must be discontinued 24h prior to QoL questionnaires assessments at time-points according to Assessment Schedule.

• Patients may receive pre-medication before the first infusion [anti histamine (diphenhydramine 50 mg or equivalent) and acetaminophen (1 g)] or patients with mild infusion reactions, may premedicate at subsequent infusions with anti-histamine (diphenhydramine 50 mg or equivalent) and acetaminophen (1 g). Patients must then be observed for at least 3 hours after each subsequent infusion before being discharged from the treatment center.

5.5.8 Prohibited treatment

Parts A and B:

Diabetes drugs, cancer drugs, immunosuppressants and biologics are not allowed.

Part C:

Cancer drugs, immunosuppressants and biologics are not allowed.

Parts B and C:

Tumor aspiration is not allowed during the treatment phase (can be performed only after 8 weeks follow-up MRI of last dose).

5.5.9 Discontinuation of study treatment and premature patient withdrawal

Study "Stopping rules"

The study will be put on hold and no further dosing will be taken pending a full safety review, if any of the following criteria are met:

- 1. 1 or more study-drug related SAEs are reported.
- 2. At least 2 patients in the active arm experience a similar AE which is assessed as either moderate or severe in intensity, and is potentially related to study-drug. Periorbital edema that resolves will not lead to study cessation, as noted above.
- 3. Only Part A: CK > 5 x ULN (CTCAE grade 3) (CTCAE, version 4.0) occurs in 2 patients on active treatment.

Individual patient withdrawal

Part A

As this is a single dose study, treatment interruption will occur only if there is evidence of an infusion reaction during study drug administration (Table 5-3).

Parts A, Part B and Part C

Patients or legal representatives may voluntarily withdraw from the study for any reason at any time. They may be considered withdrawn if they state an intention to withdraw, fail to return for visits, or become lost to follow-up for any other reason. If premature withdrawal occurs for any reason, the investigator must make every effort to determine the primary reason for a

patient's premature withdrawal from the study and record this information on the Study Completion eCRF.

Confidential

Part B and Part C

The investigator should discontinue study treatment for a given patient or withdraw the patient from the study if, on balance, he/she believes that continuation would be detrimental to the patient's well-being.

Treatment interruption will occur if there is evidence of an infusion reaction during study drug administration (Table 5-4) or any other adverse event which in the opinion of the investigator warrants discontinuation of the infusion.

Discontinuation of study treatment and patient withdrawal will be at the discretion of the Investigator, under the following circumstances:

- Infusion-related adverse event, such as hypotension, rash, or other evidence of an infusion reaction while the infusion is still running.
- Any other protocol deviation that results in a significant risk to the patient's safety.

Study treatment must be discontinued and the patient withdrawn from the study if one the following occurs:

- Patient or the legal representative withdraws consent
- Pregnancy
- Severe hypersensitivity reaction
- Drug-related SAE

Patients who discontinue prematurely the study treatment will proceed directly to the followup phase (the remaining dosing visits for these patients will be omitted).

All patients receiving MCS110 who experience a severe AE or SAE must have follow-up evaluations until resolution or stabilization of the symptoms. For patients who are lost to follow-up (i.e., those patients whose status is unclear because they fail to appear for study visits without stating an intention to withdraw), the investigator should show "due diligence" by documenting in the source documents steps taken to contact the patient, e.g., dates of telephone calls, registered letters, etc.

Part A

Patients who are prematurely withdrawn from the study (before day 29) for reasons other than safety will be replaced by an equal number of newly enrolled patients.

Part B

Patients who are prematurely withdrawn from the study before to receive 2 doses of MCS110 and perform follow-up MRI for reasons other than safety will be replaced by an equal number of newly enrolled patients.

Part C

Patients who are prematurely withdrawn from the study before to receive 3 doses of MCS110 and perform follow-up MRI for reasons other than safety will be replaced by an equal number of newly enrolled patients.

Confidential

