CL	The systemic (or total body) clearance from plasma (or serum or blood) following intravenous administration [volume / time]	
MRT	The mean residence time	
T1/2	Half life	
Tmax	The time to reach the maximum concentration after drug administration [time]	
Vss	The volume of distribution at steady state following intravenous administration [volume]	

Confidential

Glossary of terms	
Assessment	A procedure used to generate data required by the study.
Enrollment	Point/time of subject entry into the study; the point at which informed consent must be obtained (i.e., prior to starting any of the procedures described in the protocol).
Investigational drug	The study drug whose properties are being tested in the study; this definition is consistent with US CFR 21 Section 312.3 and is synonymous with "investigational new drug."
Subject number	A number assigned to each subject who enrolls in the study. When combined with the center number, a unique identifier is created for each subject in the study.
Period	A minor subdivision of the study timeline; divides phases into smaller functional segments such as screening, baseline, titration, washout, etc.
Premature subject withdrawal	Point/time when the subject exits from the study prior to the planned completion of all study drug administration and assessments; at this time all study drug administration is discontinued and no further assessments are planned.
Randomization number	A unique identifier assigned to each randomized subject, corresponding to a specific treatment arm assignment.
Stop study participation	Point/time at which the subject came in for a final evaluation visit or when study drug was discontinued whichever is later.
Study drug	Any drug administered to the subject as part of the required study procedures; includes investigational drug and any control drugs.
Study drug discontinuation	Point/time when subject permanently stops taking study drug for any reason; may or may not also be the point/time of premature subject withdrawal.
Subject	An individual who has consented to participate in this study. The term Subject may be used to describe either a healthy volunteer or a patient.
Variable	Information used in the data analysis; derived directly or indirectly from data collected using specified assessments at specified time-points.

Novartis

Confidential

Amended Protocol Version v07 (Clean) Corporate Confidential Information

Novartis

Confidential

Page 29 Protocol No. CMCS110X2201

Confidential

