5.5.5.2 Part B and Part C

Dosing adjustment due to safety issues / adverse events

In the event of a severe infusion reaction, the investigator should stop the infusion of MCS110 immediately and the patient must be discontinued from the study (Table 5-2).

Patients may receive pre-medication before the first infusion [anti-histamine (diphenhydramine 50 mg or equivalent) and acetaminophen (1 g)].

Table 5-4	Criteria for addressing infusion/hypersensitivity reactions in Part B/C
-----------	-------------------------------------------------------------------------

Toxicity	Action
CTCAE grade (value)	
Infusion-related reaction/ hypersensitivity	
Grade 1:	Maintain dose level.
transient flushing or rash, drug fever <38°C/ < 100.4°F	May premedicate at subsequent infusions with anti-histamine (diphenhydramine 50 mg or equivalent) and acetaminophen (1 g). Patients must then be observed for at least 3 hours after each subsequent infusion before being discharged from the treatment center.
Grade 2: flushing, rash, urticarial, dyspnea, drug fever ≥38.5°C/≥101.3°F	Interrupt the infusion of MCS110, administer anti-histamines or corticosteroids to be given for symptomatic relief. After recovery of symptoms, resume the infusion at a slower rate (50% of previous rate) and, if no further symptoms appear, complete the administration of the dose.
Toxicity	Action
CTCAE grade (value)	
Grade 3: symptomatic bronchospasm, with	Immediately stop MCS110 infusion and discontinue patient from study.
or without urticaria ^a ; allergy-related edema/angioedema; hypotension (characterized by a systolic pressure drop ≥ 30 mm Hg)	Medication such as anti-histamines or corticosteroids should be given for symptomatic relief.
Grade 4:	Immediately stop MCS110 infusion and discontinue
anaphylaxis ^b	patient from study.
	Epinephrine can be indicated when wheezing and anaphylaxis of acute life-threatening nature is present but should be chosen cautiously.

^{a.} Urticaria with manifestations of allergic or hypersensitivity reaction is graded as Allergic reaction/hypersensitivity.

^{b.} Anaphylaxis is defined as vascular collapse and shock (blood pressure < 90 mm Hg that is unresponsive to IV fluids) believed to be allergic in origin, with or without antecedent respiratory distress and occurring within 30 minutes of initiation of MCS110 infusion. Cutaneous manifestations include pruritus, urticaria, or angioedema.

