7.3 Pregnancies

To ensure patient safety, each pregnancy occurring after signing the informed consent must be reported to Novartis within 24 hours of learning of its occurrence. When pregnancy occurs in a patient in the study, the **study drug must be discontinued**. The occurrence of pregnancy will trigger unblinding of a given patient (see Section 14.1) for safety purposes. The pregnancy should be followed up to determine outcome, including spontaneous or voluntary termination, details of the birth, and the presence or absence of any birth defects, congenital abnormalities, or maternal and/or newborn complications. The collection of this information could last for up to 3 months following the birth of the child. Similar information will be collected if the partner of a male participant become pregnant while her partner is participating to the study.

Pregnancy should be recorded on a Clinical Trial Pregnancy Form and reported by the investigator to the local Novartis Chief Medical Office & Patient Safety Department. Pregnancy follow-up should be recorded on the same form and should include an assessment of the possible relationship to the Novartis study drug of any pregnancy outcome. Any SAE experienced during pregnancy must be reported on the SAE Report Form.

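### A Part B/C patient with a drug-related SAE or severe hypersensitivity must leave the study, not only the drug, which can cost the 8-week MRI; few patients, possibly none, are affected

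*Protocol*

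**What the plan says.** Protocol Section 5.5.9 has a mandatory list for Parts B and C, introduced by "Study treatment must be discontinued and the patient withdrawn from the study if one the following occurs". Two of its four entries are severe hypersensitivity reaction and drug-related SAE. The other two are withdrawal of consent and pregnancy.

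Section 5.5.5.2 is parallel. For a severe infusion reaction the investigator should "stop the infusion of MCS110 immediately and the patient must be discontinued from the study", and the grade 3 and grade 4 rows of Table 5-4 read "Immediately stop MCS110 infusion and discontinue patient from study".

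The sentence directly after the Section 5.5.9 list reads "Patients who discontinue prematurely the study treatment will proceed directly to the followup phase". It names no exception. The next sentence adds that patients on MCS110 with a severe AE or an SAE "must have follow-up evaluations until resolution or stabilization of the symptoms".

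The glossary separates the two ideas. Study drug discontinuation "may or may not also be the point/time of premature subject withdrawal", whereas premature withdrawal means that "at this time all study drug administration is discontinued and no further assessments are planned". Section 6 then asks that withdrawn patients be seen promptly for the visit 777 assessments, which include an MRI in Part C.

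**The concern.** The primary efficacy outcome in Parts B and C is tumor volume on MRI 8 weeks after the last dose (Sections 3.2.1 and 3.2.2). Section 5.4 foresees a Part C primary endpoint reached early, so a patient who stops before six doses can still supply one. A patient withdrawn from the study has no visit that secures that scan. The visit 777 scan is taken whenever the visit can be arranged and is not tied to the date of the last dose.

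The patients concerned are selected by toxicity, and Part C exists to find a dose as effective as 10 mg/kg with fewer side effects. SAP Section 7.1.1 leaves missing values missing. Section 5.5.9 requires replacement only for withdrawals unrelated to safety, while Section 4 leaves replacement of other non-evaluable patients to the sponsor. Scheduled safety visits end as well, although safety and tolerability is also a primary objective. Because the text does not say which rule governs, two sites could handle the same patient differently.

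**Working it through.** The plan states no figure to reproduce. The check is of the text, followed by a count.

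**1. Which rule applies**

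| Reading | Status after a drug-related SAE | 8-week MRI |
|---|---|---|
| The list governs, and the follow-up sentence covers only patients who stop treatment but stay in the study | Withdrawn; one visit 777 | Replaced by a scan at an arbitrary interval |
| The follow-up sentence governs everyone who stops treatment | Off drug, in follow-up | Kept |

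The first reading is coherent and fits the glossary, but it loses the scan. The second keeps the scan but gives no effect to the words that withdraw the patient from the study.

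**2. Timing.** Part C doses fall on Day 1 and weeks 4, 8, 12, 16 and 20 (Section 5.5.4). After six doses the target scan is at week 20 + 8 = 28, which is visit 11. If the last dose was the third, the target is week 8 + 8 = 16. Visit 777 after withdrawal has no such anchor.

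**3. Per patient** (Part C schedule under Amendment 07; the table is partly broken in the available text). For a patient withdrawn before follow-up starts, visits 10, 11, 12, 13 and 777 (weeks 24, 28, 40, 56 and 72) become one visit: 5 to 1. MRIs at visits 11, 12, 13 and 777 become one: 4 to 1. Event-driven follow-up of the SAE comes on top and is not counted here.

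**4. How many patients**

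Inputs:
- 18 Part C patients exposed and 4 drug-related SAEs in Part C (Section 1.1, Study CMCS110X2201). The number of patients behind the 4 events is not given.
- 5 Part C patients with an infusion reaction, 4 of them at the first dose; 2 cases classed as SAEs (Section 3.5.2, cut-off 19-Jan-2018).

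Patients who met the SAE trigger: 1/18 = 5.6% to 4/18 = 22.2%.

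A patient stopped at the first dose cannot supply a multiple-dose outcome under either rule. Infusion reactions that could cost such an outcome: 5 − 4 = 1.

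Ceilings, assuming one event per patient and that every eligible event fell after the first dose and before the 8-week scan:
- Both infusion SAEs among the four: (4 − 2) + 1 = 3; 3/18 = 16.7%.
- One of them among the four: (4 − 1) + 1 = 4; 4/18 = 22.2%.
- Neither among the four: 4 from the SAE trigger, 4/18 = 22.2%; with one later severe infusion reaction, 4 + 1 = 5; 5/18 = 27.8%.

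Floor: 0. The events may have come at the first dose or after the 8-week scan, or sites may have applied the follow-up sentence.

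**The case against.** **There may be no contradiction.** The glossary defines the two terms separately, and Section 5.5.9 itself distinguishes stopping treatment from withdrawal. The follow-up sentence can therefore be read as covering only patients who remain in the study. This stands: a reader might infer a flat contradiction, and the documents support only an unresolved choice. It does not rescue the MRI, because the harmonising reading is the one that loses it.

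**Pregnancy.** A reader might cite Section 7.3, which says "study drug must be discontinued", as a second conflict with the list. It is not one. That section deals with reporting and is silent on study withdrawal.

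**Size.** A reader might add the three non-serious infusion reactions (5 − 2) to the four SAEs and arrive at 7 of 18 (39%). That needs all three to have been grade 3 or 4, which is not stated. It also counts first-dose reactions, which cannot cost a multiple-dose outcome.

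**Little inference rests on the 8-week scan.** This largely stands. Part C tumor volumes are summarised descriptively, the Bayesian model and the Part C ANCOVA use week 4, and dose escalation uses week 12. Earlier MRIs and the visit 777 MRI still enter the descriptive summaries and the dose-time-response model. The waterfall plot takes the maximum reduction up to 8 weeks after the last dose. No hypothesis test is shown to be affected.

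**Safety is partly covered.** SAE follow-up to resolution or stabilization continues, and SAE reporting runs for 30 days after participation stops. What is lost is the scheduled visits.

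**It is late.** By version 07, 18 of about 19 planned Part C patients had been exposed (Sections 1.1 and 4).

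**Conclusion.** The point holds as a cheap improvement, not as a threat to the trial's conclusions. The protocol orders withdrawal from the study for a drug-related SAE or a severe hypersensitivity or infusion reaction, and nothing keeps the 8-week MRI for a patient withdrawn that way. Whether the follow-up sentence overrides this is left open.

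The number of patients affected cannot be fixed and may be zero. The ceiling is about 3 of 18 (17%) if both serious infusion reactions are among the four drug-related SAEs, and 5 of 18 (28%) if neither is. These ceilings rest on one event per patient and on event timing that the documents do not show. They also assume that the SAE and infusion-reaction counts refer to comparable data cuts; only the latter is dated. No relation to arm or dose is shown, so bias in the dose comparison is possible but not demonstrated. The benefit of a change is mainly for patients still on treatment, in follow-up or being re-dosed.

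**What to change.** In the Section 5.5.9 list, the severe-reaction sentence of Section 5.5.5.2 and the grade 3 and 4 rows of Table 5-4, replace study withdrawal for drug-related SAE and severe hypersensitivity or infusion reaction with two instructions: permanent discontinuation of study treatment, and entry into the follow-up phase. State that the MRI 8 weeks after the last dose, counted from the actual last dose, and the scheduled safety visits are kept unless consent is withdrawn. Leave every treatment-stopping trigger as it is, so no patient receives more drug.

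The cost is a wording amendment in those places and a few already-scheduled visits for patients off treatment. If the follow-up sentence was always meant to govern, the edit only makes the other passages agree with it.
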